8.3 Lost to Follow Up

A participant will be considered lost to follow-up if he or she fails to return for one or more scheduled visits and is unable to be contacted by the study site staff.

The following actions must be taken if a participant fails to return to the clinic for a required study visit:

- The site will attempt to contact the participant and reschedule the missed visit up to 7
 days after the 4 weeks from the previous visit and counsel the participant on the
 importance of maintaining the assigned visit schedule and ascertain if the participant
 wishes to and/or should continue in the study.
- Before a participant is deemed lost to follow-up, the investigator or designee will make every effort to regain contact with the participant (where possible, 3 telephone calls and if possible, 1 email). These contact attempts should be documented in the participant's medical record or study file.
- Should the participant continue to be unreachable, he or she will be considered to have withdrawn from the study with a primary reason of lost to follow-up.

9. Correlative/Special Studies

Not applicable

9.1 Laboratory Correlative Studies

9.1.1 Title – Laboratory Correlative Study #1

9.1.1.1 Collection of Specimen(s)

9.1.1.2 Handling of Specimen(s)

9.1.1.3 Shipping of Specimen(s) (if multicenter)

9.1.1.4 Site(s) Performing Correlative Study (if multicenter)

9.2 Special Studies

9.2.1 Title – Special Correlative Study #1

9.2.1.1 Assessment

9.2.1.2 Method of Assessment

9.2.1.3 Timing of Assessment

10. Measurement of Effect

PGA (Physician Global Assessment) Score:

The Principal Investigator will utilize the Physician Global Assessment (PGA) score for screening purposes during the screening/baseline visit to determine eligibility. The PGA will be comprised of five components: lamellar splitting, transverse splitting, ridging and longitudinal groove, longitudinal splitting, and nail thickness. Lamellar splitting, which represents onychoschizia, is defined as distal furrows or splits encompassing the distal nail plate involving the complete free edge of the nail plate. The second component, transverse splitting, is described as horizontal splitting from the free edge of the nail plate- with at least 2 or 3 horizontal splits of the distal nail plate. The third component, ridging and longitudinal grooves, is defined by at least 50% of the nail plate showing deep ridges and corresponding grooves. The fourth component, longitudinal splitting, which represents onychorrhexis, is defined as at least one deep longitudinal split of the entire nail plate. The fifth component, nail thickness, is defined by a clearly visible change in nail thickness. The presence of each of these components during the screening/baseline visit will represent 1 point on a scale. The inclusion criterion requires patients to have a score of at least 2 out of a maximum of 5 points. An independent blinded endpoint committee will assess change from baseline based on the PGA.

10.1 Response Criteria

Change in the PGA from baseline.

10.2 Duration of Response

Duration of overall response: The duration of overall response is measured from the time measurement criteria are met for CR or PR (whichever is first recorded) until the first date that recurrent or progressive disease is objectively documented (taking as reference for progressive disease the smallest measurements recorded since the treatment started).

The duration of overall CR is measured from the time measurement criteria are first met for CR until the first date that recurrent disease is objectively documented.

Duration of stable disease: Stable disease is measured from the start of the treatment until the criteria for progression are met, taking as reference the smallest measurements recorded since the treatment started.

10.3 Progression-Free Survival

Not Applicable.

10.4 Other Response Parameters

Please see section 12.5 Secondary Endpoints.

11. Data Reporting / Regulatory Considerations

11.1 Data Collection

The data collection plan for this study is to utilize REDCap to capture all treatment, toxicity, efficacy, and adverse event data for all enrolled subjects.

11.1.1 REDCap

REDCap (Research Electronic Data Capture) is a free data management software system that is fully supported by the Weill-Cornell Medical Center CTSC. It is a tool for the creation of customized, secure data management systems that include Web-based data-entry forms, reporting tools, and a full array of security features including user and group-based privileges, authentication using institution LDAP system, with a full audit trail of data manipulation and export procedures. REDCap is maintained on CTSC-owned servers that are backed up nightly and support encrypted (SSL-based) connections. Nationally, the software is developed, enhanced and supported through a multi-institutional consortium led by the Vanderbilt University CTSA.

11.2 Regulatory Considerations

11.2.1 Institutional Review Board/Ethics Committee Approval

As required by local regulations, the Investigator will ensure all legal aspects are covered, and approval of the appropriate regulatory bodies obtained, before study initiation.

Before initiation of the study at each study center, the protocol, the ICF, other written material given to the patients, and any other relevant study documentation will be submitted to the appropriate Ethics Committee. Written approval of the study and all relevant study information must be obtained before the study center can be initiated or the IP is released to the Investigator. Any necessary extensions or renewals of IRB approval must be obtained for changes to the study, such as amendments to the protocol, the ICF, or other study documentation. The written approval of the IRB together with the approved ICF must be filed in the study files.

The Investigator will report promptly to the IRB any new information that may adversely affect the safety of the patients or the conduct of the study. The Investigator will submit written summaries of the study status to the IRB as required. On completion of the study, the IRB will be notified that the study has ended.

All agreed protocol amendments will be clearly recorded on a protocol amendment form and will be signed and dated by the original protocol approving signatories. All protocol amendments will be submitted to the relevant institutional IRB for approval before implementation, as required by local regulations. The only exception will be when the amendment is necessary to eliminate an immediate hazard to the trial participants. In this case, the necessary action will be taken first, with the relevant protocol amendment following shortly thereafter.

Once protocol amendments or consent form modifications are implemented at the lead site, Weill Cornell Medicine, updated documents will be provided to participating sites, as applicable. Weill Cornell Medicine must approve all consent form changes prior to local IRB submission.

Relevant study documentation will be submitted to the regulatory authorities of the participating countries, according to local/national requirements, for review and approval before the beginning of the study. On completion of the study, the regulatory authorities will be notified that the study has ended.

11.2.2 Ethical Conduct of the Study

The Investigators and all parties involved should conduct this study in adherence to the ethical principles based on the Declaration of Helsinki, GCP, ICH guidelines and the applicable national and local laws and regulatory requirements.

This study will be conducted under a protocol reviewed and approved by the applicable ethics committees and investigations will be undertaken by scientifically and medically qualified persons, where the benefits of the study are in proportion to the risks.

11.2.3 Informed Consent

The investigator or qualified designee must obtain documented consent according to ICH-GCP and local regulations, as applicable, from each potential subject or each subject's legally authorized representative prior to participating in the research study. Subjects who agree to participate will sign the approved informed consent form and will be provided a copy of the signed document.

The initial ICF, any subsequent revised written ICF and any written information provided to the subject must approved by IRB prior to use. The ICF will adhere to IRB requirements, applicable laws and regulations.

11.2.4 Compliance with Trial Registration and Results Posting Requirements

Under the terms of the Food and Drug Administration Modernization Act (FDAMA) and the Food and Drug Administration Amendments Act (FDAAA), the Sponsor-Investigator of the trial is solely responsible for determining whether the trial and its results are subject to the

requirements for submission to http://www.clinicaltrials.gov. Information posted will allow subjects to identify potentially appropriate trials for their disease conditions and pursue participation by calling a central contact number for further information on appropriate trial locations and trial site contact information.

11.2.5 Record Retention

Essential documents are those documents that individually and collectively permit evaluation of the study and quality of the data produced. After completion of the study, all documents and data relating to the study will be kept in an orderly manner by the Investigator in a secure study file. Essential documents should be retained for 2 years after the final marketing approval in an ICH region or for at least 2 years since the discontinuation of clinical development of the IP. In addition, all subjects medical records and other source documentation will be kept for the maximum time permitted by the hospital, institution, or medical practice.

12. Statistical Considerations

12.1 Study Design/Endpoints

For study design, please see section 3. Study Design.

Endpoints

The Primary efficacy endpoint will be the Physician Global Improvement Assessment (PGIA), which will be compared between follow-up point (week 12 - 14) and baseline point for nails with PRP injection, and between follow-up point (week 12 - 14) and baseline point for nails without PRP injection. The power analysis estimated that with approximately 44 nails with PRP injection enrolled in the study, a score change of 0.5 from baseline to week 12 – 14 can be detected through paired two-sided t-test with 90% power at 0.05 significant level for PRP group. The calculation assumed a standard deviation of 1 in scores. PGA is a novel tool that there is not enough reference to assume an accurate standard deviation, so the sample size estimation was also performed on a range of sd assumption. With assumption of sd in range of 0.5 to 1, 13 to 97 nails would be needed for the PRP injection group to detect a score change of 0.5 from baseline to week 12 - 14 through paired two-sided t-test with 90% power at 0.05 significant level.

Sample size estimation summary given different settings of standard deviation and meaningful changes

	sd=0.5	sd=1	sd=1.5
Difference = 1	5	13	26
Difference = 0.5	13	44	97

Secondary

Subject reported assessments of nail health will be analyzed using descriptive statistics.

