Randomized Open Label Blinded Endpoint Design, i.e. Treatment

is open label with respect to patient and investigators but is blinded to the endpoint committee. 10 patients presenting que signs and symptoms of brittle nail syndrome will be included. 8 of 10 nails will be randomized to receive treatment with platelet-rich plasma, and 2 of 10 nails will receive injections with platelet-poor plasma (controls). Each patient will receive 3 treatments and high-

quality images will be taken. At the end of the study an

independent blinded endpoint committee composed of 3 experts on nail diseases will assess efficacy using the Physician Global Improvement score. Adverse effects associated to treatment will

be collected throughout the study.

Description of Sites/ Facilities Enrolling Participants:

Weill Cornell Dermatology - [name]

Weill Cornell Dermatology - East Side, [name]

Study Duration: October 2022. **Participant Duration:** 12 - 14 weeks.

Study Agent/Device Name

Intervention Description: Platelet-rich plasma (PRP), injected into the proximal nail fold

monthly for 3 months. It is defined as a device by the Food and Drug Administration (FDA), and it is a self-contained disposable kit containing two sterile blood separating vacuum tubes, two sleeve

filters, various needles and a transferring device.

Primary Objective: The primary objective of this study is to demonstrate the efficacy

of platelet-rich plasma (PRP) injections for brittle nails.

Secondary Objectives: The secondary objective of this study is to demonstrate the safety

and tolerability of PRP injections for brittle nails.

Primary Endpoints: The Primary efficacy endpoint will be the change in the Physician

Global Improvement Assessment (PGIA) of the 8 target nails from baseline to weeks 12 - 14 of follow-up to determine efficacy of

PRP injection in the treatment of brittle nail syndrome.

Secondary Endpoints: Subject reported assessments of nail health will be analyzed using

descriptive statistics.

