1.2 Study Objectives and End Points

1.2.1 Primary Objectives

The primary objective of this study is to demonstrate the efficacy of platelet-rich plasma (PRP) injections for brittle nails.

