1.2.4 Primary Endpoints

The Primary efficacy endpoint will be the change in the Physician Global Improvement Assessment (PGIA) of the 8 target nails from baseline to weeks 12 – 14 of follow up to determine efficacy of PRP injection in the treatment of brittle nail syndrome.

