3.2 Scientific Rationale for Study Design

This is a PROBE design- Prospective Randomized Open Label Blinded Endpoint Design, i.e. Treatment—is open label with respect to patient and investigators but is blinded to the endpoint committee. 8/10 Fingernails per participant will be randomized to receive treatment with plateletrich plasma and the remaining 2 nails will receive injections with platelet-poor plasma. Potential problems with the control group include nonuniform results due to the lack of response for the 2 nails receiving injections with platelet-poor plasma.

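### No PRP-versus-PPP comparison is planned: two separate before/after tests cannot separate a PRP effect from change shared by all ten nails

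*Combined protocol and SAP*

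**What the plan says.** Section 12.1 describes two comparisons of PGIA. The first is for the PRP nails, "which will be compared between follow-up point (week 12 - 14) and baseline point for nails with PRP injection". The second is for the control nails, "and between follow-up point (week 12 - 14) and baseline point for nails without PRP injection". The only named test is a paired t-test, and the power statement covers one group: a change of 0.5 "can be detected through paired two-sided t-test with 90% power at 0.05 significant level for PRP group".

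Section 1.2.4 is narrower still. It defines the primary endpoint as "the change in the Physician Global Improvement Assessment (PGIA) of the 8 target nails from baseline", with no mention of the control nails; the Protocol Summary does the same. Sections 12.4.1 and 12.4.2 only refer back to 12.1.

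The rest of the document describes a controlled experiment:

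- Section 1.2.1: "The primary objective of this study is to demonstrate the efficacy of platelet-rich plasma (PRP) injections for brittle nails".
- Section 6.1.2: each participant's ten fingernails are randomly assigned 8:2 to PRP or PPP, and PPP is labelled placebo.
- Section 3.2 treats the PPP nails as a control group and comments on it: "Potential problems with the control group include nonuniform results".
- Section 3.3 expects PRP to promote nail growth and PPP not to.

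**The concern.** A before/after change in the PRP nails is the sum of any PRP effect and whatever happens to all ten nails of that participant. This protocol has several candidates for the shared part:

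- All ten proximal nail folds are injected (7.7), so an effect of the injection itself is shared.
- Participants enter on a PGA score of at least 2 (4.2), so some drift back from a bad moment is to be expected.
- Section 2.1 lists moisturizers as treatment and 4.4 bans them during the study, so stopping them may shift every nail. Nail medication and polish are different: 3.1 has them stopped before the study starts.

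The randomised PPP nails are there so that this shared part can be subtracted, and no planned analysis subtracts it. Followed as written, the plan could credit PRP with an improvement common to all nails, or miss a PRP effect hidden by a common worsening. The stated 90% power also answers the before/after question only. No power is given for the randomised comparison.

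**Working it through.** **1. The plan's own figures.** Inputs from 12.1: paired two-sided t-test, alpha 0.05, power 90%, change 1 or 0.5, SD 0.5, 1 or 1.5. With the exact noncentral t distribution (df = n − 1, noncentrality = change × √n / SD), the smallest n values are 5, 13, 26 for a change of 1 and 13, 44, 97 for a change of 0.5. All six cells match, and n = 44 gives power 0.900. The plan's SD is therefore the SD of a nail's change, nails are treated as independent, and no control term enters.

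**2. Planned numbers.** Section 12.2 gives 10 participants, 80 PRP nails and 20 PPP nails.

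**3. No PRP effect, shared change.** Assumed: every nail changes by 0.5, SD of change 1, and ICC is the correlation of changes within a participant. The documents give neither the shared change nor an ICC.

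To keep clustering out of the question, first take the 10 participant means of the 8 PRP nails. Their SD is √(ICC + (1 − ICC)/8), and the test has 9 df. The other rows come from 200,000 simulated trials per setting.

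| Share of trials significant | ICC 0 | ICC 0.3 | ICC 0.5 |
|---|---|---|---|
| SD of participant mean | 0.354 | 0.622 | 0.750 |
| PRP before/after, 10 participant means | 97.7% | 62.0% | 46.9% |
| PRP before/after, 80 nails | 99.3% | 92.3% | 88.4% |
| PPP before/after, 20 nails | 56.4% | 56.5% | 56.4% |
| PRP significant and PPP not | 43.3% | 36.9% | 32.8% |
| PRP-minus-PPP contrast, 9 df | 5.1% | 5.0% | 5.0% |

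Row 2 shows that allowing for clustering does not cure the problem. Row 5 shows that setting the two p-values side by side does not cure it either: 80 nails against 20 produces that pattern in about a third or more of trials with no PRP effect. The plan does not adopt that rule, but a reader of two separate results might.

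**4. What the contrast can do.** For each participant, take the mean change of 8 PRP nails minus the mean change of 2 PPP nails. The participant effect cancels, so the SD of this difference is SD × √((1 − ICC)(1/8 + 1/2)). At SD 1 it is 0.791, 0.661, 0.559 and 0.433 for ICC 0, 0.3, 0.5 and 0.7. Power is for an assumed true difference of 0.5 with n = 10. The 95% CI half-width is t(0.975, 9) × SD of difference / √10.

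| SD of change | Power at ICC 0 / 0.3 / 0.5 / 0.7 | CI half-width at the same ICCs |
|---|---|---|
| 0.5 | 94% / 99% / >99% / >99% | 0.28 / 0.24 / 0.20 / 0.15 |
| 1 | 43% / 57% / 71% / 90% | 0.57 / 0.47 / 0.40 / 0.31 |
| 1.5 | 22% / 30% / 39% / 58% | 0.85 / 0.71 / 0.60 / 0.46 |

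At SD 1, 90% power would need 29, 21, 16 and 10 participants at these ICCs.

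**5. If the PRP effect varies between participants.** Step 4 assumes that it does not. Adding a variance of 0.1 to the difference at SD 1, ICC 0.3 gives an SD of √(0.4375 + 0.1) = 0.733 and lowers power from 57% to 49%. The 9-df test keeps its size at 0.050. A participant-adjusted model that omits the term (89 df) has size 0.073.

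**The case against.** The strongest replies are these.

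- *The 0.5 shared improvement is arbitrary.* It equals the effect the trial is sized for, nothing in the documents supports that value, and stopping moisturizers would more likely worsen nails. This is fair as to size. At a shared change of 0.2 the participant-mean test is significant in 36%, 15% and 12% of trials at ICC 0, 0.3 and 0.5. That is still above 5%, and a common worsening would mask a PRP effect instead.
- *The nail-level percentages mix two defects.* This is true. With no shared change at all, the 80-nail test already rejects in about 27% (ICC 0.3) and 37% (ICC 0.5), because nails are treated as independent. The participant-mean row is the clean measure of the present point.
- *Section 3.3 states two expectations, which match the two before/after comparisons.* This has some force. The case for a contrast rests more on the randomised placebo allocation in 6.1.2 and the control group in 3.2.
- *The study is small, both changes will be reported, and the contrast is underpowered.* Two within-group results are not a comparison. The documents do not call this a pilot; they claim 90% power and aim to demonstrate efficacy. Low power for the relevant question is a reason to state it, not to quote power for another question.

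None of these supplies the missing comparison.

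**Conclusion.** The concern holds and must be fixed. As written, the primary analysis makes no use of the randomised control and could be met with no PRP effect. How often depends on the size of the shared change and the ICC, both assumed here: 98%, 62% and 47% at a shared change of 0.5, and 36%, 15% and 12% at 0.2, for SD 1 and ICC 0, 0.3 and 0.5 on participant means. The contrast stays at about 5% throughout.

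That no PRP-versus-PPP analysis is planned rests on the text alone. The contrast powers rest on an assumed PRP-minus-PPP difference of 0.5 (the plan uses 0.5 only as a change from baseline), an assumed ICC range, and no variation of the PRP effect between participants. They are therefore on the favourable side. The SD is uncertain by the plan's own account: "there is not enough reference to assume an accurate standard deviation".

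**What to change.** **Section 12.1, primary analysis.** For each participant, compute the mean change of the 8 PRP nails minus the mean change of the 2 PPP nails. Test the 10 differences with a two-sided one-sample t-test (9 df), and report the mean difference with its 95% CI. A mixed model with participant and participant-by-treatment effects is an acceptable alternative, but one analysis must be named in advance. The t-test is the simpler choice and does not depend on a degrees-of-freedom rule. The two before/after changes become descriptive.

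**Protocol Summary and section 1.2.4.** Define the primary endpoint as the difference between PRP and PPP nails.

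**Power statement in 12.1.** Restate it for this contrast with 10 participants, over SD 0.5 to 1.5 and a stated ICC range, and present the result as an estimate with its CI.

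**Precondition.** There must be one numeric score per nail. Section 3.1 describes PGIA as observed improvement, sections 10 and 10.1 use change in PGA, and no rule combines the three raters. If PGIA is scored directly as improvement, use the week 12–14 score in place of the change. The paired t-test now planned needs the same clarification, so this is not an extra cost of the contrast.

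**Cost.** For the contrast itself, wording in three places, with no new data, visits or change of allocation. The sample size can stay at 10 if the aim is an estimate with a CI. The price is that the 90% power claim no longer stands unless the SD is near 0.5 or the ICC is high (about 0.7 at SD 1).

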4.1 Study Population

Subjects with a diagnosis of brittle nail syndrome in all 10 fingernails who meet the inclusion and exclusion criteria will be eligible for participation in this study.

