7.11 Measures to Minimize Bias: Randomization and Blinding

Computer software will be used to randomly generate a randomization table. 8/10 fingernails will be randomly allocated to treatment with PRP and the remaining 2 fingernails will receive injections with PPP. Randomization for each participant will be done on the same day of their first treatment, after all inclusion and exclusion criteria, including a negative histopathology report for onychomycosis are fulfilled. For the present study, treatment will be open label with respect to patient and investigators but is blinded to the endpoint committee. High quality images will be obtained utilizing a Canon camera and reviewed by an independent blinded endpoint committee (3 dermatologists with expertise in nails disease [name], [name], and [name] [name]) for PGIA (Physician Global Improvement Assessment.

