12.2 Sample Size/Accrual Rate

With a total of 10 participants, 80 fingernails will be included in the treatment group, and 20 fingernails in the control group.

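### The sample size and the paired t-test count nails as independent, but the 80 PRP nails come from 10 people, so the stated 90% power and 0.05 level do not hold

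*Combined protocol and SAP*

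**What the plan says.** Section 12.1 compares the PGIA at weeks 12 to 14 with baseline, separately for nails with and without PRP. It states that "with approximately 44 nails with PRP injection enrolled in the study, a score change of 0.5" from baseline "can be detected through paired two-sided t-test with 90% power at 0.05 significant level for PRP group". On variability it says "The calculation assumed a standard deviation of 1 in scores", and a table gives the number of nails for three SDs and two differences.

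Section 12.2 turns this into people: "With a total of 10 participants, 80 fingernails will be included in the treatment group, and 20 fingernails in the control group". Section 7.11 gives the structure within each person: "8/10 fingernails will be randomly allocated to treatment with PRP and the remaining 2 fingernails will receive injections with PPP".

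Section 12.4.1, on the primary analysis, only refers back to 12.1, and 12.3 marks stratification as not applicable. No ICC, design effect, random effect, GEE or participant-level summary appears anywhere in the document.

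**The concern.** The 80 PRP nails are 10 clusters of 8. There are good reasons to expect the changes within a person to be correlated. Section 4.1 restricts entry to "Subjects with a diagnosis of brittle nail syndrome in all 10 fingernails", so one disease process affects all of them. All PRP nails of a person receive plasma from that person's own blood (7.5, 7.6). They also share that person's adherence to the restrictions on polish, moisturizers and medication (4.4), and the same visits and photographs (6.1.2).

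Pairing baseline with follow-up deals with correlation within one nail over time. It does nothing about correlation among 8 nails of one person. If that correlation is ignored, the standard error of the mean change is too small, confidence intervals are too narrow, and the primary test rejects too often when nothing has changed. The primary objective is to demonstrate efficacy (1.2.1), so this error falls on the trial's main claim.

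**Working it through.** **Inputs.** From 12.1: paired t-test, two-sided alpha 0.05, power 90%, change 0.5, SD 1, 44 nails. From 12.2 and 7.11: 10 participants, 8 PRP nails each, 80 in all. The ICC of the nail changes is not in the documents and is an assumption, shown over a range.

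**1. The plan's own figures.** Exact paired (one-sample) t-test power from the noncentral t distribution, with n independent nails and the SD taken as the SD of the change, gives these sizes for 90% power:

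| | SD 0.5 | SD 1 | SD 1.5 |
|---|---|---|---|
| Difference 1 | 5 | 13 | 26 |
| Difference 0.5 | 13 | 44 | 97 |

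All six cells match the table in 12.1, and power at n = 44 is 90.0%. The calculation therefore treats each nail as an independent unit. It also uses 1 as the SD of the change. If 1 were the SD of a single score, 44 would require a baseline to follow-up correlation of 0.5.

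**2. Design effect.** With 8 nails per person, DE = 1 + (8 − 1) × ICC = 1 + 7 × ICC.

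- The 80 nails are worth 80/DE independent nails: 80/1.7 = 47 at ICC 0.1, 80/3.1 = 26 at 0.3, 80/4.5 = 18 at 0.5.
- Even on the plan's own count, 80/DE ≥ 44 requires ICC ≤ (80/44 − 1)/7 = 0.117.

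**3. Type I error of the nail-level test.** Simulation with no true change: 10 × 8 nails, normal changes with equal correlation within a person, one-sample t-test on 79 df, at least 40,000 runs per ICC. Repeat runs agreed to within about one percentage point. The result does not depend on the SD.

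**4. Power of a valid test.** The mean change over one participant's 8 PRP nails has SD = √((1 + 7 × ICC)/8) when the SD of change is 1: 0.461, 0.622 and 0.750 at ICC 0.1, 0.3 and 0.5. A t-test on 10 such means has 9 df, and its detectable change at 90% power is 1.1546 × SD.

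| ICC | Type I error, nail-level test | Power for 0.5, 10 participant means | Change detectable at 90% | Participants for 90% power at 0.5 |
|---|---|---|---|---|
| 0.05 | 9% | 93% | 0.47 | 10 |
| 0.1 | 13% | 86% | 0.53 | 12 |
| 0.3 | 27% | 62% | 0.72 | 19 |
| 0.5 | 37% | 47% | 0.87 | 26 |

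(At ICC 0.05: SD = √(1.35/8) = 0.411, and 1.1546 × 0.411 = 0.47.)

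The participant-level test keeps its 5% level throughout. Its power for 0.5 stays at 90% only up to ICC 0.07, and at 80% only up to about 0.15.

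**5. The nail-level test is not rescued by its rejection rate.** At ICC 0.3 it rejects about 92% of the time when the change is 0.5, but also about 27% of the time when there is no change. The first figure is therefore not valid power.

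**6. The PPP comparison.** The same fault affects the 20 control nails (2 per person), less severely: type I error is about 9% at ICC 0.3 and 11% at ICC 0.5.

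**The case against.** The strongest reply is that the loss of power depends on an unknown ICC and on one cell of the plan's table. The study has 80 PRP nails, not 44, and this slack absorbs some clustering. For the participant-level test with 10 people, the other cells give:

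- Difference 0.5 with SD 0.5, or difference 1 with SD 1: 90% power holds up to ICC of about 0.71.
- Difference 1 with SD 0.5: power is above 90% at every ICC.
- Difference 1 with SD 1.5: 90% holds up to ICC of about 0.24.
- Difference 0.5 with SD 1.5: power is about 76% even at ICC 0. Clustering is not the cause there, because the plan's own 97 nails exceed the 80 available.

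These figures are right, and the power statement should be read as conditional on SD and ICC. But difference 0.5 with SD 1 is the case on which the plan rests its 90%, and there the slack runs out at ICC 0.07. Nor does the slack protect the 0.05 level: inflation appeared at every positive ICC tried, whatever the SD.

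It can also be said that the t-test is named only in the sample-size sentences, so nail-level testing is partly inferred. It is, however, the only test the plan names, and the primary analysis section points to that text. Finally, the simulation assumes normal changes with equal correlation, whereas the PGA in section 10 is a 0 to 5 count. That may move the percentages somewhat. It does not remove the clustering.

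**Conclusion.** The concern holds and should be put right before analysis. The plan's sample size is exact arithmetic for independent nails, and its design does not supply independent nails. With SD of change 1, the primary test as written has a true type I error of about 13% to 37% for ICC 0.1 to 0.5. Valid power for a change of 0.5 with 10 participants falls from 86% to 47% over the same range. The ICC is an assumption. Only a value of essentially zero would preserve the 0.05 level, and that is implausible when one person's nails share the disease, the plasma, the habits and the photographs. The power figures also rest on the SD of 1 being that of the change. The failure of the test level does not.

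**What to change.** **Analysis (12.1, 12.4.1).** Make the participant the unit of analysis. For each participant, average the change from baseline over the PRP nails, and separately over the PPP nails. Run each within-group comparison as a one-sample t-test on the 10 participant means (9 df). Alternatively, fit a linear mixed model to the nail changes with a participant random intercept and small-sample degrees of freedom. Choose one as primary in advance.

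**Power (12.1, 12.2).** Replace the claim of 44 nails and 90% power with power for 10 participants over a stated ICC range. For the PRP change of 0.5 with SD of change 1, this is 86%, 62% and 47% at ICC 0.1, 0.3 and 0.5. State that the SD is that of the change, and label the existing table as valid only for independent nails. These figures apply to the within-PRP change. A PRP-minus-PPP contrast within person would need its own calculation.

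**Cost.** Wording in the statistical section and a less favourable power figure. No added visits or procedures, and no extra enrolment, provided the sponsor accepts the restated power. Keeping 90% at a change of 0.5 would instead take 12, 19 or 26 participants at those ICCs.
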